3.4 End of Study Definition

A participant is considered to have completed the study if he or she has completed all phases of the study including follow-up visit which is the standard of care imaging preformed after treatment. This follow-up visit does not require that the patient physically comes back for an in-trial procedure. The end of the study is defined as completion of the last visit or procedure shown in the SoA.

4. Subject Selection

4.1 Study Population

Subjects with a diagnosis of metastatic prostatic adenocarcinoma who meet the inclusion and exclusion criteria will be eligible for participation in this study.

4.2 Inclusion Criteria

Subjects must meet all of the following criteria to be enrolled in this study:

- Aged 21 years or older and below 100 years of age.
- Signed written informed consent and willingness to comply with protocol requirements.
 - Histologically confirmed diagnosis of metastatic prostate cancer
- Staging imaging exam confirming metastatic disease, e.g. total body MRI, or CT chest/abdomen/pelvis, 99mTc bone scan, NaF PET.

4.3 Exclusion Criteria

- Laboratory values:
 - Serum creatinine >2.5 mg/dL
 - AST (SGOT) >2.5x ULN
 - Bilirubin (total) >1.5x ULN
 - Serum calcium >11 mg/dL
- Presence of any other co-existing condition which, in the judgment of the investigator, might increase the risk to the subject.
- Presence of serious systemic illness, including: uncontrolled inter-current infection, uncontrolled malignancy, significant renal disease, or psychiatric/social situations, which might limit compliance with study requirements.
- Other severe acute or chronic medical condition(s) or laboratory abnormality(ies) that may increase the risk associated with study participation or investigational product administration or may interfere with the interpretation of study results and in the judgment of the investigator, would make the patient inappropriate for entry into this study.
- Inability to lay on the scanner table for the required period of time, e.g., due to bone pain or claustrophobia.

4.4 Lifestyle Considerations

No specific patient preparation is required before injection. One intravenous catheter (Hep-Lock) will be placed by staff in the CBIC or WCINYP. This will remain in place for the duration of the encounter.

4.5 Screen Failures

Screen failures are defined as participants who consent to participate in the clinical trial but are not subsequently entered in the study. A minimal set of screen failure information is required to ensure

transparent reporting of screen failure participants, to meet the Consolidated Standards of Reporting Trials (CONSORT) publishing requirements and to respond to queries from regulatory authorities. Minimal information includes demography, screen failure details, eligibility criteria, and any serious adverse event (SAE).

4.6 Strategies for Recruitment and Retention

Patients will be recruited through the outpatient clinics of the Department of Radiation Oncology and Genitourinary Medicine at WCMC. Members of the treatment team and research staff will screen their patient's medical records for suitable research study participants and discuss the study and their potential for enrolling in the research study. Potential subjects contacted by their treating physician will be referred to the investigator/research staff of the study. If the investigator is a member of the treatment team, s/he will screen their patients' medical records for suitable research study participants and discuss the study and their potential for enrolling in the research study. Potential subjects contacted by their treating physician will be referred to the investigator/research staff of the study. During the initial conversation between the investigator/research staff and the patient, the patient may be asked to provide certain health information that is necessary to the recruitment and enrollment process. The investigator/research staff may also review portions of their medical records in order to further assess eligibility. They will use the information provided by the patient and/or medical record to confirm that the patient is eligible and to contact the patient regarding study enrollment. If the patient turns out to be ineligible for the research study, the research staff will destroy all information collected on the patient during the initial conversation and medical records review, except for any information that must be maintained for screening log purposes. In most cases, the initial contact with the prospective subject will be conducted either by the treatment team, investigator or the research staff working in consultation with the treatment team.

Patients will be required to sign a statement of informed consent that meets the requirements of the code of Federal Regulations (11) and the IRB of this center. A consent form is appended. The medical record will include a statement that written informed consent was obtained (and document in the record the date written consent was obtained before) and the patient is enrolled in the study.

5. Registration Procedures

5.1 Subject Registration (WCM only)

Subjects will be registered within the WRG-CT as per the standard operating procedure for Subject Registration.

6. Study Procedures

6.1 Schedule of Assessments

Table 1. Schedule of trial events

	Screening- Visit 1 (Baseline or D0)	Imaging 1* (Visit 2 or D1)	Imaging 2* (Visit 3 or D2)
ICF	X		
Medical History	X		
Physical Exam	X		X
Review medications	X		
CBC	X		
Serum BUN and Creatinine	X		
AST, ALT, ALP, bil, albumin	X		
Review of prior imaging	X		
Adverse event monitoring		X	X
⁶⁸Ga-PSMA administration		X	X
⁶⁸Ga-PSMA PET scans		X	X
Research Blood draws **		X	X

*Two scans with ⁶⁸Ga-PSMA-cyclotron and ⁶⁸Ga-PSMA-generator radiotracers will be performed at least 24h apart (max 48h)
 
** Research blood draws will be performed only in a subset of patients (3-5) and are not required for participation in the study. The planned timepoints are as follows: pre tracer injection, 5 minutes (+/- 10 minutes) 15 minutes (+/- 10 minutes), 30 minutes (+/-10 minutes), 60 minutes (+/-10 minutes). A blood draw will also be performed after each scan (12 blood draws in total per patient at most) (for details refer to section 6.1.2.2).
			

6.1.1 Screening Visit

Once a patient signs informed consent, but prior to the initiation of neoadjuvant ADT for prostate cancer the following standard of care tests and procedures will be performed prior to the administration of the investigational diagnostic agent:

- Obtain written informed consent
- Obtain medical history
- Physical exam including Karnofsky performance status
- Confirm adequate venous access
- Review medications
- Laboratory studies:
 - CBC, Serum BUN and creatinine, AST, ALT, alkaline phosphatase, bilirubin and albumin
- Review of prior imaging studies to confirm metastatic disease status (e.g. 99mTc bone scan (prostate cancer), NaF PET (prostate cancer), MRI, or CT)

6.1.2 Intervention Phase

6.1.2.1 Patient scans

Two ⁶⁸Ga-PSMA PET/CT scans will be performed successively at least 6 hours apart.

6.1.2.2 Serum Blood Draws

A subset of patients will have serum blood draws (approximately 5 ml) for pharmacokinetic analysis. This is **only** required in a subset (3-5 patients) as a smaller number of patients will be needed to generalize organ and lesional dosimetry. The planned timepoints are as follows: pre tracer injection, 5 minutes (+/- 10 minutes) 15 minutes (+/- 10 minutes), 30 minutes (+/-10 minutes), 60 minutes (+/-10 minutes). A blood draw will also be performed after each scan (12 blood draws in total per patient at most). This will be done through the IV placed to administer the PET tracer during the imaging visit. Apart from routine laboratory tests, samples will also be evaluated for the presence of ⁶⁸Ga, as well as ⁶⁶Ga, potential contaminants for generator-produced and cyclotron-produced products. Blood counts, liver function tests, and creatinine levels will also be monitored before, during, and after imaging evaluation/radiotracer injection. Apart from routine laboratory tests, samples will also be evaluated for the presence of ⁶⁸Ga, as well as ⁶⁶Ga, potential contaminants for generator-produced and cyclotron-produced radiotracers, respectively. Images will also be evaluated for location of radiotracer uptake, as well as excretion and organ-specific dosimetry.

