7.1 Study Intervention/Patient scans

Protocol initiation quality assurance

Patient scans will be acquired on one of the Siemens Biograph mCT™ PET/CT scanners with a preference for the same instrument on all scans. Quality assurance images from each system will be acquired at the beginning of the protocol on all mCT scanners using a ^{68}Ga -filled 20-cm-diameter cylindrical water phantom with average SUVs in the range $1.0 \pm 0.5 \text{ g/ml}$ with no artifacts on visual inspection.

Individual patients preferably use the same scanner system for both scans.

Prior to imaging evaluation, patients will be permitted to eat a light meal.

An intravenous catheter (Hep-Lock) will be placed in the CBIC or WCINYP for radiopharmaceutical administration, scans, and blood sampling.

Patient scans

Two dynamic whole body ^{68}Ga -PSMA PET/CT scans will be performed successively at least 6 hours apart. As there will be an accumulation of activity in the urinary bladder, patients will have pre-treatment hydration and encourage voiding immediately prior to imaging, however the short half-life of ^{68}Ga should not result in imaging counts from the first scan to appear on the latter scan.

PET/CT imaging patients will be positioned on a flat couch in radiation treatment position. Custom-made immobilization devices, skin markings, PET/CT gantry, and room lasers will be used to ensure accurate and reproducible positioning. Imaging will start with low-dose CT scan (80 mA) for attenuation correction, followed by a PET scan. A low dose CT scan (80 mA) will be performed over the prostate or a pre-determined index lesion. A 10min dynamic PET scan at the pelvic bed position, centered over the prostate tissues, will be initiated concurrently with an intravenous bolus injection of approximately 2.5MBq/kg of body weight ($\pm 10\%$) of ^{68}Ga -PSMA, followed by a time series of whole-body PET scans (passes) at least 10-75 min and at most 10-90 min post injection. The PET acquisition time per bed position per pass will be fixed at 30sec and the total number of passes summed post acquisition to produce the static ^{68}Ga -PSMA PET images will be at least six. The total number of late passes may be increased, if needed, such that the product of total acquisition time per bed position from all passes and injected activity is at least 7.5 MBq/kg*min or a total acquisition time of 90min is reached.

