Moreover, the number of bed positions will be adjusted to cover a field of view from top of the skull to mid-thigh of an average human adult for each pass. All PET scans will be conducted with patients in a supine position with the arms comfortably positioned and secured by the side of the patient. All whole-body PET passes of each subject will be uni-directional, i.e. they will be performed along the same axial direction (cranio-caudal or caudo-cranial).

The PET data from at least the last six whole-body scan passes will be summed up and reconstructed at each bed position such that the product of total acquisition time per bed position from all passes and injected activity is at least 7.5 MBq/kg*min or a total scan time of 90min is reached. The resulting composite static PET images will then be combined with the same method as that employed for conventional static PET images at each bed position and the composite Standardized Uptake Value (SUV) static PET images will be calculated. In the meantime, the dynamic ⁶⁸Ga-PSMA concentration in the blood plasma (input function) will also be derived from the dynamic PET images at the pelvis, as estimated from the 0-10min p.i. of the initial dynamic pelvic PET scan and the corresponding pelvic beds of the subsequent set of whole-body PET passes. For that purpose, regions of interest will be drawn in the lumen of the abdominal section of the descending aorta that is included in the pelvic bed position. The blood pool image regions will be drawn as far as possible from the neighboring aortic wall to minimize any partial volume effects. The image derived input function data will then be fitted to the measured blood samples data for validation and enhanced accuracy. Subsequently, the images from all the dynamic PET whole-body passes and the image-derived input function will be fitted to the Patlak graphical model on a voxel-by-voxel basis to produce whole-body ⁶⁸Ga-PSMA net uptake rate constant (Ki) images. During the PET scan procedure, the patient will be allowed to get off from the couch in between the dynamic whole-body passes, if required (such as for a bathroom break).

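### The ±10 min draw windows allow a 5-minute blood sample before injection and let early samples overlap, with no rule that actual draw times are recorded or used

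*Combined protocol and SAP*

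**What the plan says.** Section 6.1.2.2 lists the timed draws as "pre tracer injection, 5 minutes (+/- 10 minutes) 15 minutes (+/- 10 minutes") and "30 minutes (+/-10 minutes), 60 minutes (+/-10 minutes"). One further draw follows each scan, up to "12 blood draws in total per patient at most". The footnote to the schedule in Section 6.1 gives the same times and tolerances, so neither place corrects the other.

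The sampling is limited and optional: "Research blood draws will be performed only in a subset of patients (3-5) and are not required for participation in the study". Its stated purpose is pharmacokinetic: "A subset of patients will have serum blood draws (approximately 5 ml) for pharmacokinetic analysis". Section 3.1 counts basic pharmacokinetics as part of the comparison of the two production methods.

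Section 7.1 gives the samples a second use. The plasma input function for the Patlak model comes from the PET images, "as estimated from the 0-10min p.i. of the initial dynamic pelvic PET scan" and from the pelvic beds of the later passes. Blood comes in after that: "The image derived input function data will then be fitted to the measured blood samples data for validation and enhanced accuracy". The dynamic scan "will be initiated concurrently with an intravenous bolus injection", which fixes time zero.

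No section says that the actual draw time is recorded, that it replaces the nominal time in any fit, or that draws must keep their order. Section 11.1 does not mention draw times, and Section 12 contains no pharmacokinetic analysis.

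**The concern.** A tolerance of 10 minutes is twice the first nominal time and equal to the gap between the first two. It therefore cannot keep the 5-minute draw after injection or keep the two earliest draws apart. Blood concentration can be expected to change fastest in this part of the curve.

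Two uses of the samples are exposed. The first is the within-patient pharmacokinetic comparison of the cyclotron and generator products. The windows apply afresh at each scan, so a sample with the same label can be taken at quite different times for the two products, and a timing difference could pass for a product difference. The second is the blood-based check and refinement of the image-derived input function. Section 3.3 puts plasma activity in the denominator of Ki, so a mistimed sample treated as correctly timed could carry into Ki, the quantity in both exploratory objectives. With 3-5 patients sampled, timing errors cannot be relied on to average out.

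**Working it through.** **Inputs.** Nominal times of 5, 15, 30 and 60 min, each ±10 min (Sections 6.1 and 6.1.2.2); one pre-injection and one post-scan draw per scan; two scans; time zero at the bolus, where the 0-10 min dynamic scan also starts (Section 7.1). The early blood half-life is not in the documents; 5-20 min is an assumption.

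**The plan's own figure.** (1 pre-injection + 4 timed + 1 post-scan) × 2 scans = 12 draws, which matches the stated maximum. The schedule has been read as intended.

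**Windows (nominal time ± 10, minutes from injection).**

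| Draw | Window | Overlap with next draw |
|---|---|---|
| 5 min | -5 to 15 | 5 to 15 (10 min) |
| 15 min | 5 to 25 | 20 to 25 (5 min) |
| 30 min | 20 to 40 | none |
| 60 min | 50 to 70 | – |

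**What these windows permit.**

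- Before injection: 5 of the 20 min in the 5-minute window, or 25%. A sample taken there repeats the separate pre-injection draw and contains no tracer from that injection.
- Order: the 5- and 15-minute draws can coincide or reverse anywhere between 5 and 15 min. The 15- and 30-minute draws can do so between 20 and 25 min.
- Worst case: the 5-minute draw at -5, the 15-minute draw at 25, and the 30-minute draw no earlier than 25. The first post-injection sample is then at 25 min, and none falls within the 0-10 min dynamic scan.

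**Illustration only.** Assume independent draw times, uniform over each window.

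- Reversal needs the 5-minute draw in 5 to 15 (0.5), the 15-minute draw in 5 to 15 (0.5), and the wrong order within that range (0.5): 0.5 × 0.5 × 0.5 = 12.5%.
- Neither draw within 0-10 min: 0.5 × 0.75 = 37.5%.

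The documents do not say how draws will actually be spread over the windows.

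**Size of a timing error, if nominal times are used.** For exponential decline, factor = 2^(timing error / half-life). For a 10-min error:

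| Assumed half-life | Factor |
|---|---|
| 5 min | 2^(10/5) = 4.0 |
| 10 min | 2^(10/10) = 2.0 |
| 15 min | 2^(10/15) = 1.6 |
| 20 min | 2^(10/20) = 1.4 |

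Between products the extreme is wider. A 15-minute sample at 5 min for one product and 25 min for the other differs by 20 min, a factor of 2^(20/20) = 2 to 2^(20/5) = 16 on the same assumption. If actual times enter the fit, these errors vanish; what remains is the possible lack of early samples.

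**Half-width that would work.** For a common half-width w:

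- 5-minute draw after injection: 5 - w > 0, so w < 5.
- 5- and 15-minute windows apart: 5 + w < 15 - w, so w < 5.
- 15- and 30-minute windows apart: 15 + w < 30 - w, so w < 7.5.
- 30- and 60-minute windows apart: 30 + w < 60 - w, so w < 15.

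The stated w = 10 fails the first three.

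**The case against.** The strongest reply is that little depends on these samples. Section 7.1 builds the input function from the images, starting at the bolus, and uses blood only to validate and refine it. Most of the up to 30 patients will have no blood samples, whatever the windows. Section 7.1 takes biodistribution from the PET data, and Section 6.1.2.2 also evaluates images for excretion and organ dosimetry. The primary comparison of SUVmean and SUVmax, with its 30% criterion in Section 12, uses no blood data. All of this stands and limits the reach of the point.

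A second reply is that a window governs collection and does not set the time used in analysis, so an off-nominal sample with a recorded time is still usable. This is also correct. Silence does not show that times go unrecorded, since the case report form is not among the documents. But no provision requires recording or use, so the safeguard cannot be assumed.

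A third reply is that staff would not take the 5-minute sample before injection, because a pre-injection draw is already listed. That is probably so in practice. The overlap of the 5- and 15-minute windows, however, needs no such odd reading.

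A reader might go further and infer that the early input function is undefined, that the secondary dosimetry comparison rests only on the sampled subset, or that one misplaced sample would change the trial's result. The documents support none of these. The early curve is defined from images, dosimetry also draws on images, and Section 12 has no decision rule that uses blood concentrations.

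**Conclusion.** The windows are wrong as written, in both places where they appear. They guarantee neither an early post-injection sample nor the order of the first samples, and no rule on actual times makes up for this. As a result, the sampled early blood curve may not be comparable between the two products, and the blood-based check of the image-derived input function is unreliable in the optional subset of 3-5 patients.

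The interval arithmetic is exact and needs no assumption beyond reading the times as minutes from injection. The factor of 1.4-4.0 is a conditional worst case: it needs nominal times in the analysis, a full 10-min deviation and an assumed half-life of 5-20 min. The impact is confined to secondary and exploratory analyses. The image-derived input function itself and the primary SUV comparison are not affected.

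**What to change.** In Sections 6.1 and 6.1.2.2, replace the uniform ±10 min with windows that start after injection and do not overlap. A common half-width has to be under 5 min; windows set separately for each time point would also serve and could leave the 60-minute draw as it is. State in the same places, and in Section 7.1, that the exact draw time relative to injection is recorded at each scan and that this time, not the nominal one, is used in the pharmacokinetic and input-function fits.

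The cost is a wording change in these sections and a draw-time field on the case report form if it lacks one. The downside is tighter draw timing for the 3-5 patients in the subset. Recording and using actual times removes most of the potential error by itself, but only narrower windows secure an early sample. The change should be made before sampling starts, because a sample whose draw time was not recorded cannot be placed on the curve later.

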6.1.3 Evaluation during intervention

Performance Status

Performance status will be assessed using the Karnofsky Performance Status scale.

Vital Signs

Blood pressure and heart rate will be obtained prior to each PET scan.

Serum Blood Draws

As described above

6.1.4 Follow- up

The patients that are enrolled in the study will afterwards undergo treatment for metastatic prostate cancer disease either as per standard of care or after enrollment in clinical trials. During completion of the treatment, there is usually a follow- up scan approximately 3mo after treatment where additional imaging is performed. This additional imaging will be considered the follow- up visit and will be used to correlate imaging with reported outcomes as well as biochemical and genomic analysis.

7. Study Intervention

7.1 Study Intervention/Patient scans

Protocol initiation quality assurance

Patient scans will be acquired on one of the Siemens Biograph mCT™ PET/CT scanners with a preference for the same instrument on all scans. Quality assurance images from each system will be acquired at the beginning of the protocol on all mCT scanners using a ^{68}Ga -filled 20-cm-diameter cylindrical water phantom with average SUVs in the range $1.0 \pm 0.5 \text{ g/ml}$ with no artifacts on visual inspection.

Individual patients preferably use the same scanner system for both scans.

Prior to imaging evaluation, patients will be permitted to eat a light meal.

An intravenous catheter (Hep-Lock) will be placed in the CBIC or WCINYP for radiopharmaceutical administration, scans, and blood sampling.

Patient scans

Two dynamic whole body ^{68}Ga -PSMA PET/CT scans will be performed successively at least 6 hours apart. As there will be an accumulation of activity in the urinary bladder, patients will have pre-treatment hydration and encourage voiding immediately prior to imaging, however the short half-life of ^{68}Ga should not result in imaging counts from the first scan to appear on the latter scan.

PET/CT imaging patients will be positioned on a flat couch in radiation treatment position. Custom-made immobilization devices, skin markings, PET/CT gantry, and room lasers will be used to ensure accurate and reproducible positioning. Imaging will start with low-dose CT scan (80 mA) for attenuation correction, followed by a PET scan. A low dose CT scan (80 mA) will be performed over the prostate or a pre-determined index lesion. A 10min dynamic PET scan at the pelvic bed position, centered over the prostate tissues, will be initiated concurrently with an intravenous bolus injection of approximately 2.5MBq/kg of body weight ($\pm 10\%$) of ^{68}Ga -PSMA, followed by a time series of whole-body PET scans (passes) at least 10-75 min and at most 10-90 min post injection. The PET acquisition time per bed position per pass will be fixed at 30sec and the total number of passes summed post acquisition to produce the static ^{68}Ga -PSMA PET images will be at least six. The total number of late passes may be increased, if needed, such that the product of total acquisition time per bed position from all passes and injected activity is at least 7.5 MBq/kg*min or a total acquisition time of 90min is reached.

Moreover, the number of bed positions will be adjusted to cover a field of view from top of the skull to mid-thigh of an average human adult for each pass. All PET scans will be conducted with patients in a supine position with the arms comfortably positioned and secured by the side of the patient. All whole-body PET passes of each subject will be uni-directional, i.e. they will be performed along the same axial direction (cranio-caudal or caudo-cranial).

The PET data from at least the last six whole-body scan passes will be summed up and reconstructed at each bed position such that the product of total acquisition time per bed position from all passes and injected activity is at least 7.5 MBq/kg*min or a total scan time of 90min is reached. The resulting composite static PET images will then be combined with the same method as that employed for conventional static PET images at each bed position and the composite Standardized Uptake Value (SUV) static PET images will be calculated. In the meantime, the dynamic ⁶⁸Ga-PSMA concentration in the blood plasma (input function) will also be derived from the dynamic PET images at the pelvis, as estimated from the 0-10min p.i. of the initial dynamic pelvic PET scan and the corresponding pelvic beds of the subsequent set of whole-body PET passes. For that purpose, regions of interest will be drawn in the lumen of the abdominal section of the descending aorta that is included in the pelvic bed position. The blood pool image regions will be drawn as far as possible from the neighboring aortic wall to minimize any partial volume effects. The image derived input function data will then be fitted to the measured blood samples data for validation and enhanced accuracy. Subsequently, the images from all the dynamic PET whole-body passes and the image-derived input function will be fitted to the Patlak graphical model on a voxel-by-voxel basis to produce whole-body ⁶⁸Ga-PSMA net uptake rate constant (Ki) images. During the PET scan procedure, the patient will be allowed to get off from the couch in between the dynamic whole-body passes, if required (such as for a bathroom break).

The PET data will be used to determine the repeatability of the multi-parametric (SUV and Ki) features of the ⁶⁸Ga-PSMA organ biodistribution between two successive ⁶⁸Ga-PSMA-generator and cyclotron PET/CT scans. Moreover, the same data will be utilized to evaluate the equivalence of the SUV and Ki features between the organ biodistributions of generator- and cyclotron-produced ⁶⁸Ga-PSMA radiopharmaceuticals as estimated from respective dynamic whole-body ⁶⁸Ga-PSMA PET/CT scans. Following standard image processing, regions of interest (ROI) will be drawn on the summed dynamic image data set, and then copied onto the individual dynamic frames, in order to analyze the tumor activity as a function of time. Reconstructed whole body static ⁶⁸Ga-PSMA PET images will be analyzed on a standard workstation.

After 24-48 hours, patients will be asked to repeat PET imaging after injection of the second experimental radiotracer. The same procedures will apply. The radiopharmacy will keep a log of all doses administered. The intravenous catheter will be removed at the conclusion of imaging.

